11.1.1. Subject Death

All subject deaths must be reported by the investigator to Medtronic as soon as possible after the investigator first learns of the death. Document the adverse event that led to the subject death on an Adverse Event form. Further supporting evidence that is not originally provided by the site may be requested by Medtronic to aid in the adjudication of the death.

A copy of the death certificate, if available and allowed by state/local law, should be sent to the Medtronic. When a death occurs in a hospital, a copy of the death summary report and all relevant hospital records should be sent to the Medtronic, if available. If an autopsy is conducted, the autopsy report should also be sent to the Medtronic if available and allowed by state/local law. When the death occurs at a remote site, it is the investigative site's responsibility to attempt retrieval of information about the death. In summary, the following data will be collected:

- Date of death
- Detailed description of death
- Cause of death
- Relatedness to system and/or procedure
- Death summary/hospital records (if available and allowed by local law)
- Autopsy report (if available and allowed by local law)
- Death certificate (if available and/or allowed by local law)

11.2. Reporting of Adverse Events and Device deficiencies

Adverse Events will be recorded and reported according to local regulatory requirements and are outlined in Table 8. It is the responsibility of the Investigator to abide by the adverse event reporting requirements stipulated by local law and the sites' Ethics Committee. Investigators are required to evaluate and document all AEs and Device Deficiencies (per the definitions in Table 6) observed in study subjects from the time they enrolled (signed the ICF) until they are no longer participating in the study. AEs and Device Deficiencies should be collected for both the study device as well as for the comparator. AEs should be followed until one of these criteria is met:

- Until the AE resolves
- Until no further action can be taken for an ongoing AE
- Until the subject exits the trial, or
- Until trial closure

NOTE: In the case of permanent impairment, continue to follow the event until it stabilizes and the overall clinical outcome has been ascertained.

The investigator is not required to classify USADE.

11.3. Emergency contact details

For emergency contact regarding a SAE and/or SADE, investigators should contact their Medtronic clinical study representative or monitor immediately (refer to the study contact list provided in the site's study documents binder/investigator site file or refer to the contact information provided on the title page). A list of contact information will be kept separately.

AE Reporting Requirements

Table 8: AE reporting Requirements

For the following events, reporting requirements are: 
• Serious Adverse Events (SAE)	
Investigators shall immediately adopt appropriate therapeutic measures for subjects, and simultaneously report to the management department of medical device clinical study in clinical Research institutions in written form. Management department of medical device clinical study shall report to:	
Medtronic	Immediately
Local food and drug regulatory authority and health and family planning regulatory authority of the province, autonomous region and municipality directly under the central government where the clinical Research institution locates	Within 24 hours
Ethics Committee	Within 24 hours/per EC's requirements
For the following events, reporting requirements are: 
• All other AEs• All other Device Deficiencies	
Investigators shall record all the adverse events and device deficiencies occurred during the clinical study. Investigators shall analyze the reasons for the events with Medtronic and document the analysis result in written report, including the comments of continuing. Suspending or terminating study, which shall be reported to the Ethics Committee through management department of medical device clinical study in clinical Research institutions for review.	
To Medtronic	Submit in a timely manner after the investigator first learns of the event.
To Ethics Committee	Per EC's requirements
For the following events, reporting requirements are: 
• Serious Adverse Events (SAE)• DD with SAE potential	
Medtronic submits to:	
The food and drug regulatory authorities and health and family planning competent authorities at the same level	Within 5 working days upon being informed
Other clinical Research institutions and investigators participating in the study	As per local reporting requirement

Ethics Committee	Timely report to EC of the clinical Research institution through management department of medical device clinical study
------------------	---

12. Statistical Design and Methods

Osteoporotic vertebral compression fractures (OVCFs) have gradually evolved into a serious health care problem globally. In order to reduce the morbidity of OVCF patients and improve their life quality, two minimally invasive surgery procedures, vertebroplasty (VP) and balloon kyphoplasty (BKP), have been developed. Both VP and BKP require the injection of bone cement into the vertebrae of patients to stabilize fractured vertebra. As such, bone cement as the filling material plays an essential role in the effectiveness of these treatments. The study will randomize subjects into two arms the Xpede and the Mendec as comparative products. The Mendec Bone Cement has been launched on China Market and has very similar composition material with the Kyphon®Xpede™ Bone Cement and they are both polymethylmethacrylate (PMMA).

Due to these reasons the design of this study is a non-inferiority based on the margin δ as the maximum acceptable extent of clinical non-inferiority of Kyphon®Xpede™ Bone Cement.

Since there are two primary efficacy endpoints, the overall sample size will be determined by the primary objective that requires the larger sample size. The non-inferiority hypothesis on the NRS requires 154 subjects and including 15% of potential loss-to-follow-up, the total sample size for the study will be 178 randomized subjects by 1:1 randomization schedule. If we use $3 * 3 * 2$ strata, the sample size should be 180 to be divisible of 18. Considering an average of 1.35 level per patient (FREE trial 72% with 1 level, 21% with 2 levels, 7% with 3 levels¹⁰), we should have around 243 levels treated on 180 patients. Since the sample size on Angulation lead to 200 levels, and therefore to 162 subjects, the sample size will be 180 subjects. The study is considered as a success if both primary objectives are met.

¹⁰ Jan Van Meirhaeghe, Leonard Bastian, Steven Boonen, Jonas Ranstam, John B. Tillman, Douglas Wardlaw, on behalf of the FREE investigators. A Randomized Trial of Balloon Kyphoplasty and Nonsurgical Management for Treating Acute Vertebral Compression Fractures. SPINE Volume 38, Number 12, pp 971–983

13. Sample size determination

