Where: t is 24 weeks (6 months), μ_X is the NRS mean score in the Xpede arm, μ_M is the NRS mean score in the MENDEC and "m" is the non-inferiority margin.

Based on this statistical test and assuming a one-sided type I error rate of 0.025 and a type II error rate of 0.20 or equivalently, power of 0.80 for the final analysis, it will be claimed that Xpede is not inferior to MENDEC with respect to NRS score if the upper bound of the two-sided 95% confidence interval of the difference ($\mu_X(t) - \mu_M(t)$) is less than the margin.

Thus, the non-inferiority hypothesis will require a sample size of 152 (76 per arm) subjects and including 15% of potential loss-to-follow-up, the total sample size for the study will be 179. If we use 3 * 3 * 2 strata, the sample size should be 180 to be divisible of 18 (90 per arm).

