Based on this statistical test and assuming a one-sided type I error rate of 0.025 and a type II error rate of 0.20 or equivalently, power of 0.80 for the final analysis, it will be claimed that XPEDE is not inferior to MENDEC with respect to Angulation if the upper bound of the two-sided 95% confidence interval of the difference ($\mu_X(t) - \mu_M(t)$) is less than the margin. Thus, the non-inferiority hypothesis will require a sample size of 160 levels treated and including 20% of potential loss-to-follow-up, the total sample size for the study will be 200 levels treated (100 per arm). Using the same distribution of treated levels from FREE trial: 72% with 1 level, 21% with 2 levels, 7% with 3 levels, the required subjects will be $200/1.35 = 148$. If we use $3 * 3 * 2$ strata, the sample size should be 162 to be divisible of 18 (81 per arm), which is smaller than what is required for the first primary objective.

Balloon kyphoplasty versus non-surgical fracture management for treatment of painful vertebral body compression fractures in patients with cancer: a multicentre, randomised controlled trial. Lancet Oncol 2011; 12: 225–356

Medtronic Confidential

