The analysis on the second primary endpoint based on Index Vertebral Body Angles will use multiple data points per patient according to the number of levels treated. Assuming not completely independence among measures within same patient the analysis will be performed by means of Generalized Estimating Equation (or mixed models for repeated measures) using patient as the subject. The model will have the Index Vertebral Body Angles as dependent variables and baseline value, number of level treated (as the multiple data points) and arm as explanatory variables. All assumptions for regression models will be assessed by viewing plots of the residual values. It will be claimed that XPEDE is not inferior to MENDEC with respect to Angulation if the upper bound of the two-sided 95% confidence interval of the difference ($\mu_X(t) - \mu_M(t)$) is less than the margin.

The overall study is considered reached if both the null NI hypotheses are rejected. A separate Statistical Analysis Plan (SAP) will be developed prior to data being analyzed to further describe statistical methods, pre-specified data handling rules, and pre-specified analyses that will be included in the final study reports. Any deviation from the pre-specified statistical analyses will be noted in the study report.

The Statistical Analysis Plan will include a comprehensive description of the statistical methods and analyses to be included in reports that include analysis of endpoints. Any change to the data analysis methods described in the CIP will require an amendment only if it changes a principal feature of the CIP. Any other change to the data analysis methods described in the CIP, and the justification for making the change, will be described in the clinical study report.

14. Ethics

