6.1. Primary Endpoint on NRS

The following assumptions were used for the determination of the sample size for NRS non-inferiority hypothesis:

- The NRS score which ranges from 0 to 10 is assumed to be approximately normally distributed.
- The NRS score is to be assessed at 24 weeks (6 months) after the procedure.
- The NRS at 24 weeks (6 months) is expected to be 3.5 in the MENDEC Spine treatment, and 3.5 or more in the Xpede. A difference in NRS score of 1.5 or less is considered clinically unimportant for this comparison. It is considered the maximum acceptable increase in NRS score compared to the MENDEC Spine arm.
- The standard deviation of the NRS score is expected to be approximately 3.27 for each treatment. Common standard deviation will be assumed for both arms.
- The sample size should be sufficient to produce an 80% chance (power) of a significant result at a one-sided 0.025 significance level.

The non-inferiority hypothesis on the NRS requires 152 subjects and including 15% of potential loss-to-follow-up, the total sample size for the study will be 179 randomized subjects by 1:1 randomization schedule. Since there are strata, the sample size should be 180 to be divisible of 18 strata, i.e. 90 patients per arm. If we use $3 * 3 * 2$ strata, the sample size should be 180 to be divisible of 18. Considering an average of 1.35 level per patient (FREE trial 72% with 1 level, 21% with 2 levels, 7% with 3 levels²), we should have around 243 levels treated in 180 patients.

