6.2. Primary Endpoint on Vertebral Body Angles

The following assumptions were used for the determination of the sample size for VBA non-inferiority hypothesis:

- The Angulation is assumed to be approximately normally distributed.
- The Angulation is to be assessed at 24 weeks (6 months) after the procedure.
- The Angulation at 24 weeks (6 months) is expected to be 1.2 in the MENDEC Spine treatment, and 1.2 or more in the XPEDE. A difference in Angulation of 2.5 or less is considered clinically unimportant for this comparison (half standard deviation rule). It is considered the maximum acceptable increase in Angulation compared to the MENDEC Spine arm. Standard deviation of 5.0 at 1 month from CAFÉ study was conservatively used to derive the non-inferiority margin of 2.5.
- The standard deviation of the Angulation is expected to be approximately 5.6 for both arms. Standard deviation of 5.6 at 12 months from CAFÉ study³ was conservatively used as the standard deviation for both arms.
- The sample size should be sufficient to produce an 80% chance (power) of a significant result at a one-sided 0.025 significance level.

The non-inferiority hypothesis on the Vertebral Body Augmentation assuming 20% of potential loss-to-follow-up, the total sample size for the study will be 148 randomized subjects by 1:1 randomization schedule. Since there are strata, the sample size should be 162 to be divisible of 18 strata, i.e. 81 patients per arm.

Since final sample size was determined to be 180 patients, i.e. 90 patients per arm.

7. Statistical Methods

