7.9.1.2. Primary Endpoint on Vertebral Body Angles

The primary endpoint on Vertebral Body Angles (VBA) is the mean change of Index Vertebral Body Angles from baseline at 6 months in the subjects treated with Kyphon®Xpede™Bone Cement compared with subjects treated with Mendec Spine Bone Cement. It will be claimed that XPEDE is not inferior to MENDEC with respect to Vertebral Body Angles if the upper bound of the two-sided 95% confidence interval of the difference (Mean Vertebral Body Angles in the XPEDE arm at 6 months - Mean Vertebral Body Angles in the MENDEC arm at 6 months) < 2.5.

X-ray images will be reviewed by independent radiological reviewers who will be blinded to the subjects' treatment groups for each analysis. Adjudications provided both by the site and by the independent reviewers will be analyzed separately. Final conclusion will be made according to independent reviewer adjudication.

The analysis will be performed by means of Generalized Estimating Equation (or mixed models for repeated measures) using patient as the subject. The model will have the Index Vertebral Body Angles as dependent variables and baseline value, number of levels treated (as the multiple data points), type of procedure and arm as explanatory variables. All assumptions for regression models will be assessed by viewing plots of the residual values.

As sensitivity analysis, comparison will be also performed by t-test on:

1. the average value of VBA for the 3 separate treated levels;
2. the value of VBA for all the 3 pooled treated levels.

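### Protocol Section 12 gives the pain-score sample size as 154/178 where the rest of the plan gives 152/179, and the 148 subjects for the angle reach 80% power only if levels within a patient are uncorrelated; N = 180 stands

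*Protocol*

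**What the plan says.** **NRS.** Protocol Section 12 says the hypothesis "requires 154 subjects and including 15% of potential loss-to-follow-up, the total sample size for the study will be 178 randomized subjects". Protocol 13.1.2 says it "will require a sample size of 152 (76 per arm) subjects", which becomes 179 after the 15% loss. SAP 6.1 agrees with 13.1.2: the hypothesis "requires 152 subjects and including 15% of potential loss-to-follow-up, the total sample size for the study will be 179 randomized subjects". All three places then round to 180, a multiple of the 18 strata.

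**Angle.** Protocol 13.2.2 says the hypothesis "will require a sample size of 160 levels treated and including 20% of potential loss-to-follow-up", giving 200 levels. Dividing by 1.35 levels per patient gives 148 subjects, rounded to 162 for the strata. SAP 6.2 has the same chain: "assuming 20% of potential loss-to-follow-up, the total sample size for the study will be 148 randomized subjects", then 162. Section 12 quotes 162; the synopsis stops at 148. None of these steps allows for correlation between levels. The analysis text does: Protocol 13.4 opens its account of the angle model with "Assuming not completely independence among measures within same patient", and SAP 7.9.1.2 specifies a "Generalized Estimating Equation (or mixed models for repeated measures) using patient as the subject".

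**Success rule.** Protocol Section 12 says "the overall sample size will be determined by the primary objective that requires the larger sample size". Each endpoint is sized alone at 80% power, one-sided 0.025 (Protocol 13.1.2 and 13.2.2, SAP 6). Success requires both (synopsis, Protocol 12 and 13.4, SAP 7.9.1). Neither document gives a power for that combined rule.

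**The concern.** One protocol version carries two incompatible NRS calculations, and a reader cannot tell which one supports 180. This matters because 154 inflated in the way that 13.1.2 inflates 152 would exceed 180.

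For the angle, the sample-size section counts each treated level as a full independent observation, while the analysis section of the same protocol says that levels in a patient are not fully independent. If levels are positively correlated, 148 subjects carry less information than 160 independent levels, and the stated 80% is not delivered at that number.

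A third, lesser matter is that the plan gives 80% for each endpoint and a rule that needs both, but leaves the chance of meeting both unreported. What is at stake there is a missed non-inferiority claim, not a false one.

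**Working it through.** **Inputs from the documents.** One-sided alpha 0.025, target power 0.80, true difference taken as 0. NRS: margin 1.5, SD 3.27, loss 15%. Angle: margin 2.5, SD 5.6, loss 20%. Patients with 1, 2 or 3 levels: 72%, 21%, 7%. Power is from the noncentral t with 2n − 2 degrees of freedom and noncentrality margin / (SD·√(2/n)), n per arm.

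**Step 1: NRS size.**

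| Total evaluable | Power | Divided by 0.85 |
|---|---|---|
| 150 | 0.797 | 176.5 → 177 |
| 152 | 0.802 | 178.8 → 179 |
| 154 | 0.807 | 181.2 → 182 |

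The pair 152/179 reproduces exactly. The pair 154/178 does not: 154 is not the minimum, and 178 × 0.85 = 151.3, fewer than the 154 it is meant to protect. The figure 178 is consistent with 154 × 1.15 = 177.1, rounded up, but the documents do not show how it was obtained.

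**Step 2: angle size as stated.** 158 levels give 0.796 and 160 give 0.801. Then 160/0.80 = 200 and 200/1.35 = 148.1. The plan's figure reproduces, with levels treated as independent.

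**Step 3: angle size with correlated levels.** The documents give no ICC, so every value here is an assumption. Mean levels = 0.72 + 2(0.21) + 3(0.07) = 1.35. Mean of squares = 0.72 + 4(0.21) + 9(0.07) = 2.19, and 2.19/1.35 − 1 = 0.622. With N subjects and 20% loss, the effective number of levels is:

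- equal weighting (GEE, independence working correlation): N × 0.8 × 1.35 / (1 + 0.622·ICC)
- efficiently weighted mixed model: N × 0.8 × [0.72 + 0.42/(1 + ICC) + 0.21/(1 + 2·ICC)]

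Angle power, before any gain from baseline adjustment (equal / efficient):

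| ICC | 148 subjects | 162 subjects | 180 subjects |
|---|---|---|---|
| 0 | 0.801 | 0.835 | 0.872 |
| 0.1 | 0.777 / 0.778 | 0.813 / 0.814 | 0.852 / 0.853 |
| 0.2 | 0.753 / 0.759 | 0.790 / 0.797 | 0.831 / 0.837 |
| 0.5 | 0.686 / 0.717 | 0.726 / 0.756 | 0.770 / 0.799 |

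The ICC at which power falls to 0.80 is about 0.004 for 148 subjects, 0.16 / 0.18 for 162 and 0.35 / 0.49 for 180. At an assumed ICC of 0.2, the subjects needed for 160 effective levels after 20% loss are 166.6 / 163.9.

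**Step 4: both endpoints.** At N = 180 with the full losses, NRS has 180 × 0.85 = 153 subjects (power 0.805) and the angle has 180 × 1.35 × 0.8 = 194.4 levels (power 0.872 at ICC 0). With independent endpoints and no baseline adjustment, the power for both is 0.805 × 0.872 = 0.70. Changing one assumption at a time:

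| Change | Power for both |
|---|---|
| Endpoint correlation 0.3 / 0.5 / 0.8 (assumed) | 0.72 / 0.74 / 0.77 |
| ICC 0.2 (assumed) | 0.67 |
| ICC 0.5 (assumed) | 0.62 to 0.64 |
| Loss 10% on both endpoints | 0.827 × 0.908 = 0.75 |
| No loss | 0.864 × 0.934 = 0.81 |
| NRS SD 1.3 or 1.63 (6-month values cited in Protocol 13.1.1) | about 0.87 |

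**The case against.** The case on the other side is substantial. The NRS conflict does not affect the trial: every version ends at 180, and 13.1.2 and the SAP agree. The 148 is an intermediate figure in 13.2.2 and SAP 6.2, raised to 162 for the strata and overtaken by 180. The ICC limit of 0.004 at 148 mostly reflects that 160 levels was chosen to only just clear 80%. The plan never claims 80% for meeting both endpoints, and sizing each alone and taking the larger number is stated openly.

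Most of this stands, and it limits the point. It does not remove the two textual faults: Section 12 carries a pair that the rest of the plan contradicts, and 148 is presented as delivering 80% without the independence assumption it needs.

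Three stronger readings are tempting and unsupported:

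- **That the trial has only 70% power.** The 0.70 requires all the conditions of step 4. It straddles 80% once the loss or the NRS SD is varied. Protocol 13.1.2 chose 3.27 as the highest cited value. It is also the SD of the score, whereas SAP 7.9.1.1 makes the change from baseline primary, and the documents give no SD for that change.
- **That 180 is too small for the angle.** No ICC is given, and 180 tolerates 0.35 to 0.49.
- **That 154 is right and N must rise.** 154/0.85 = 182 would force the next multiple of 18, which is 198, but the plan's own inputs yield 152.

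**Conclusion.** Two statements are wrong as written. Section 12's 154/178 conflicts with 152/179 in Protocol 13.1.2 and SAP 6.1, and only the latter follows from the plan's inputs. The angle figure of 148 subjects delivers its stated 80% only for uncorrelated levels, against the plan's own analysis assumption. The loss of power at 148 is about 2 percentage points at an assumed ICC of 0.1, 4 to 5 at 0.2 and 8 to 11 at 0.5. At 180, no shortfall is shown.

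The unreported power of the both-endpoints rule is an omission worth filling, not an error. A reader might infer from it that alpha needs adjusting; it does not, because both tests must succeed. Severity is minor: N, margins, alpha and analysis are unaffected. Confidence in the arithmetic is high. The ICC and endpoint-correlation values are assumptions throughout.

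**What to change.** 1. **Protocol Section 12:** replace 154/178 by 152/179. N stays 180.
2. **Synopsis, Protocol 13.2.2 and SAP 6.2:** state that 160 levels, or 148 subjects, assumes uncorrelated levels within a patient. Restate the requirement with an openly assumed ICC and a named working model; at an ICC of 0.2 this is about 167 subjects with equal weighting or about 164 under an efficient mixed model, both within 180.
3. **Optional, Protocol Section 12 and SAP 6:** report the power to meet both endpoints, about 70% at N = 180, with every condition attached (zero true difference, SDs 3.27 and 5.6, losses of 15% and 20%, independent endpoints, uncorrelated levels, no baseline adjustment). Add a short sensitivity table over endpoint correlation, ICC, loss and NRS SD, including 1.3 and 1.63. Note that 3.27 is the SD of the score and not of its change from baseline.

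The cost is text only. The drawback is that the ICC and endpoint correlation must be assumed in the open, and that the combined power will look less favourable than 80% under the cautious inputs.
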